6.2 Patient demographics/other baseline characteristics

All Baseline assessments should be performed prior to first study drug administration. These may occur during the Screening period or at the Baseline Visit depending on the assessment ([Table 6-1](#)).

6.2.1 Demographics

Patient demographic data to be collected on all patients include: date of birth, sex, race, ethnicity, height, weight and child-bearing potential (for females only).

6.2.2 Psoriasis medical history / previous psoriasis therapies

Patient's disease history will be collected at the Screening Visit. The information to be collected and entered as "psoriasis history" and "prior psoriasis therapies" includes the following:

- Date of first diagnosis of psoriasis prior to the Baseline Visit (by a physician).

- Previous treatments of psoriasis (including previous use of topical or systemic therapies as well as phototherapy and/or photochemotherapy) and the reason for discontinuation.
- Presence of PsA and the date of first diagnosis (by a physician).

6.2.3 Smoking history

The current and/or previous use of tobacco products will be recorded, as well as the approximate consumption per year. Non-smokers will be advised not to start smoking during the study.

6.2.4 Co-morbidities – cardiovascular medical history

Any information pertaining to cardiovascular medical history assessed prior to Screening should be reported as cardiovascular history in the eCRF. Cardiovascular risk factors should also be recorded.

6.2.5 Relevant medical history / current medical conditions

Relevant medical history and current medical conditions (not including psoriasis or PsA) present prior to signing the ICF will be recorded in the Medical History eCRF. Whenever possible, diagnoses and not symptoms will be recorded.

Patients with Crohn's Disease are eligible for the study but should be followed closely.

Significant findings that are observed after the patient has signed the ICF and that meet the definition of an AE must be recorded in the AE summary pages.

6.2.6 Prior and concomitant medications

Prior medications taken within the 6 months preceding the study Screening Visit (Visit 1), any other relevant medication taken before 6 months at the discretion of the Investigator and any concomitant medication irrespective of the start date will be captured in the eCRF.

6.2.7 Determination of tuberculosis status

Determination of TB status will be required before administration of study drug and should be performed as defined by local guidelines. TB status must be determined by medical history, signs, symptoms, and TB testing (via the QFT ([Section 6.2.7.1](#))).

Any significant findings will be recorded in the eCRF, as necessary.

6.2.7.1 QuantiFERON TB-Gold In-Tube assay

[figure not shown]
A QFT will be performed to assess the TB status at Screening for all patients. This test will only be used to determine patient's eligibility for the study. The test will be used to screen the patient population for latent TB infection ([Doherty et al 2008](#)).

This blood-based assay is specific for *Mycobacterium tuberculosis* and is not influenced by previous *Bacillus Calmette-Guérin* vaccination or exposure to other *Mycobacteria* species. This test, in contrast to the purified protein derivative skin test, is also insensitive to a booster effect since the patient is not exposed to the vaccine. The assay measures the production of interferon-gamma and presents it relative to a negative and a positive control sample ([Manuel](#)

and Kumar 2008). The QFT will be supplied by the central laboratory. Details on the collection, shipment of samples and reporting of results by the central laboratory are provided to Investigator/qualified study center staff in the laboratory manual (see Figure 6-1).

- If the test result is negative, the patient may be enrolled
- If the test result is positive, the Investigator should perform workup for the test result as per local procedures. If a TB workup was conducted prior to Screening the patient, results of the workup can be used to assess eligibility provided the workup was conducted within 12 weeks prior to Baseline.
 - Patients **positive** for latent TB per workup may be enrolled in the study if sufficient treatment has been initiated according to local routine clinical practice and will be maintained for the prescribed duration. Patients **positive** for active TB per workup are not eligible for the study.
 - Patients **negative** for TB (no signs of latent or active TB) per workup may be enrolled in the study.
- If the test result is **indeterminate**, it is **recommended to repeat the test once**. The Investigator may decide to skip the repetition of the test and proceed directly to the workup (but this is not recommended). If a TB workup was conducted prior to Screening the patient, results of the workup can be used to assess eligibility if the workup was conducted within 12 weeks prior to Day 1 (Baseline Visit).
 - If the second test is **negative**, the patient may be enrolled.
 - If the second test is **positive or indeterminate**, the Investigator should perform the work up as per local guidelines. The patient will not be eligible for enrollment if:
 - “active TB is present “or
 - if “latent TB is present” and is untreated as per local guidelines.Patients negative for TB per workup (no signs of latent or active TB) may be enrolled into the study if the workup was conducted within 12 weeks prior to Day 1 (Baseline Visit).
- If eligibility is being assessed with only 1 test result and a TB workup (i.e. no second TB test will be performed), the TB test to assess eligibility must have been done via the central laboratory for the study within the Screening period (within 4 weeks prior to Day 1 [Baseline Visit]) and the TB workup will only be considered if it was completed within 12 weeks prior to Baseline. Patients who are positive for latent TB per workup may be enrolled to the study if sufficient treatment has been initiated according to local routine clinical practice and will be maintained for the prescribed duration. Patients positive for active TB per workup are not eligible for the study. Patients negative for TB per workup (no signs of latent or active TB) may be enrolled in the study.

Figure 6-1 Tuberculosis screening flowchart

Abbreviations: TB: tuberculosis, QFT: QuantiFERON[®] TB-Gold In-Tube test

The patient will not be eligible for enrollment if “active TB is present” or if “latent TB is present and is untreated as per local guidelines.”

* If the first QuantiFERON[®] TB-Gold In-Tube test is indeterminate, the Investigator may choose to perform a second test or refer the patient for TB workup per local guidelines.

** If the result of any QuantiFERON[®] TB-Gold In-Tube test is “positive” or the results of 2 sequential tests are “indeterminate,” the patient must be referred to have a TB workup per local guidelines (if no workup within 12 weeks prior to enrollment is available).

6.2.8 Other Baseline characteristics

Baseline characteristic data to be collected for all patients includes (all laboratory tests are performed centrally except where indicated; see also [Table 6-1](#)) the following:

- Vital signs, hematology, clinical chemistry, urine, fasting lab tests (glucose, lipid panel, HbA1c and hsCRP), physical examination, height, weight, past medical history record of HIV, hepatitis B virus, and hepatitis C virus history. A urine pregnancy test will be performed for women of child-bearing potential.
- Baseline efficacy assessments of IGA mod 2011, PASI and BSA.
- Baseline PRO assessments of DLQI, EQ-5D[®], NRS (itching, scaling and pain VAS), HAQ[®]-DI (only for patients with concomitant PsA), TSQM and PBI.
- [REDACTED]

6.3 Treatment exposure and compliance

All doses of study drug administration will be recorded in the eCRF. Patient compliance to the study drug should be assessed by qualified study center personnel at each study visit using the study kits and documentation regarding study drug dispensation and administration.

Compliance will also be assessed continuously during the conduct of the study by Novartis study personnel using medication kits and corresponding documentation. Study drug doses and corresponding dates of self-administration at home should be documented in a self-administration log. Patients are required to return the self-administration log as well as all dispensed study drug at every visit back to the study center for a compliance check.

6.4 Efficacy

All efficacy assessments should be performed prior to administration of the study drug.

6.4.1 Investigator's global assessment (IGA mod 2011)

The IGA mod 2011 will be conducted for overall psoriatic disease as indicated in the assessment schedule in [Table 6-1](#). It is recommended that the same evaluator conducts the assessment throughout the study wherever possible.

The IGA mod 2011 used in this study is static, i.e. it refers exclusively to the patient's disease state at the time of the assessments, and does not attempt a comparison with any of the patient's previous disease states, whether at Baseline or at a previous visit.

The IGA mod 2011 rating scale for overall psoriatic disease is shown in [Table 6-3](#).

Patients require an IGA mod 2011 score at Baseline of 3 or 4 in order to participate in the study. Based on this scale, a patient will be considered as an IGA 0 or 1 responder if they achieve a score of 0 or 1 and improve by at least 2 points on the IGA scale at a given time point compared to their score at Baseline.

The IGA mod 2011 score will be recorded in the eCRF.

[figure not shown]

Table 6-3 The IGA mod 2011 rating scale

Score	Short description	Detailed description
0	Clear	No signs of psoriasis. Post-inflammatory hyperpigmentation may be present.
1	Almost clear	Normal to pink coloration of lesions; no thickening; no to minimal focal scaling.
2	Mild	Pink to light red coloration; just detectable to mild thickening; predominantly fine scaling.
3	Moderate	Dull bright red, clearly distinguishable erythema; clearly distinguishable to moderate thickening; moderate scaling.
4	Severe	Bright to deep dark red coloration; severe thickening with hard edges; severe / coarse scaling covering almost all or all lesions.

Note: Involvement of nails is not part of the assessment

6.4.2 Assessment of psoriasis area and severity index (PASI) and total body surface area (BSA)

The Investigator or trained qualified designee will complete the PASI assessment as indicated in [Table 6-1](#). Whenever possible, the same evaluator should perform this assessment at all visits. The total BSA affected by plaque-type psoriasis will be estimated from the percentages of areas affected, including head, trunk, upper limbs and lower limbs (see below for full details of the PASI assessment). The following calculations will be done: each reported percentage will be multiplied by its respective body region corresponding factor (head = 0.1, trunk = 0.3, upper limbs = 0.2, lower limbs = 0.4). The resulting 4 percentages will be added to estimate the total BSA affected by plaque-type psoriasis.

The PASI score ([Fredriksson and Pettersson 1978](#); [Weisman et al 2003](#); [Gottlieb et al 2006](#)) will be derived as indicated in [Table 6-4](#). The head, trunk, upper limbs and lower limbs are assessed separately for erythema, thickening (plaque elevation, induration), and scaling (desquamation). The average degree of severity of each sign in each of the 4 body regions is assigned a score of 0-4. The area covered by lesions on each body region is estimated as a percentage of the total area of that particular body region. Further practical details to help with the assessment are provided below:

1. The neck is assessed as part of the head.
2. The axillae and groin are assessed as part of the trunk.
3. The buttocks are assessed as part of the lower limbs.
4. When scoring the severity of erythema, scales should not be removed.

Because the head and neck, upper limbs, trunk and lower limbs correspond to approximately 10%, 20%, 30% and 40% of the BSA, respectively, the PASI score is calculated using the formula:

$$\text{PASI} = 0.1 (E_H + I_H + D_H)A_H + 0.2 (E_U + I_U + D_U)A_U + 0.3 (E_T + I_T + D_T)A_T + 0.4 (E_L + I_L + D_L)A_L$$

The keys for the letters are provided in [Table 6-4](#).

PASI scores can range from a lower value of 0, corresponding to no signs of psoriasis, up to a theoretic maximum of 72.0. The Baseline value for analysis of PASI is collected at Day 1

(Baseline Visit). Patients require a total BSA affected by plaque-type psoriasis of $\geq 10\%$ and a PASI score of $\geq 10\%$ at Baseline to be eligible for this study.

Table 6-4 The PASI scoring system

Body region	Erythema (E)	Thickening (plaque elevation, induration, I)	Scaling (desquamation, D)	Area score (based on true area %, A)*
Head (H) [†]	0=none	0=none	0=none	0=no involvement
	1=slight	1=slight	1=slight	1=>0-<10%
	2=moderate	2=moderate	2=moderate	2=10-<30%
	3=severe	3=severe	3=severe	3=30-<50%
	4=very severe	4=very severe	4=very severe	4=50-<70%
				5=70-<90%
				6=90-100%
Trunk (T) [‡]	0=none	0=none	0=none	0=no involvement
	1=slight	1=slight	1=slight	1=>0-<10%
	2=moderate	2=moderate	2=moderate	2=10-<30%
	3=severe	3=severe	3=severe	3=30-<50%
	4=very severe	4=very severe	4=very severe	4=50-<70%
				5=70-<90%
				6=90-100%
Upper limbs (U)	0=none	0=none	0=none	0=no involvement
	1=slight	1=slight	1=slight	1=>0-<10%
	2=moderate	2=moderate	2=moderate	2=10-<30%
	3=severe	3=severe	3=severe	3=30-<50%
	4=very severe	4=very severe	4=very severe	4=50-<70%
				5=70-<90%
				6=90-100%
Lower limbs (L) [§]	0=none	0=none	0=none	0=no involvement
	1=slight	1=slight	1=slight	1=>0-<10%
	2=moderate	2=moderate	2=moderate	2=10-<30%
	3=severe	3=severe	3=severe	3=30-<50%
	4=very severe	4=very severe	4=very severe	4=50-<70%
				5=70-<90%
				6=90-100%

* Percentage (not score) of body region (not whole body) affected will be entered in the eCRF.

[†] Neck is assessed as part of the Head (H) body region.

[‡] Axillae and groin are assessed as part of the Trunk (T) body region.

[§] Buttocks are assessed as part of the Lower limbs (L) body region.

6.4.3 Definitions of efficacy variables based on PASI

The following definitions will be used in this study based on the EMA guideline on clinical investigation of medicinal products indicated for the treatment of psoriasis (CHMP/EWP/2454/02 corr):

- **PASI 50 response (partial response):** patients achieving $\geq 50\%$ improvement (reduction) in PASI score compared to Baseline are defined as PASI 50 responders.
- **PASI 75 response:** patients achieving $\geq 75\%$ improvement (reduction) in PASI score compared to Baseline are defined as PASI 75 responders.

- **PASI 90 response:** patients achieving $\geq 90\%$ improvement (reduction) in PASI score compared to Baseline are defined as PASI 90 responders.
- **PASI 100 response / remission:** complete clearing of psoriasis (PASI = 0).

6.4.4 Appropriateness of efficacy assessments

All evaluation tools used in this study have been used previously in clinical trials for psoriasis. Evaluation of disease severity based on clinical scoring is commonly used in dermatology.

6.5 Safety

From Day 1 (Baseline Visit), all blood draws and safety assessments must be performed as indicated in [Table 6-1](#) prior to study drug administration. Appropriate safety assessments (e.g. evaluation of AEs and SAEs) should be repeated after the dose of study drug is administered.

- Evaluation of all AEs and SAEs including injection site hypersensitivity reactions, vital signs, laboratory assessments and occurrence of infections (see [Section 7](#)).
- Physical examination.
- Vital signs.
- Height and weight.
- Laboratory evaluations (hematology, clinical chemistry, urine dipstick).
- Fasting laboratory tests (glucose, lipid profile, HbA1c and hsCRP).
- Pregnancy and assessments of fertility.

6.5.1 Physical examination

A physical examination, including general appearance, will be performed as indicated in [Table 6-1](#).

If indicated, based on medical history and/or symptoms, additional examinations will be performed at the discretion of the Investigator.

If possible, assessments for an individual patient should be performed by the same member of the study center staff throughout the study.

Information for all physical examinations must be included in the source documentation at the study center. Significant findings that are present prior to the patient signing informed consent must be included in the eCRF. Significant findings made after the signing of the informed consent which meet the definition of an AE must be recorded on the eCRF ([Section 7](#)).

6.5.2 Vital signs

Vital signs (including blood pressure and pulse measurements) will be assessed as indicated in [Table 6-1](#). After the patient has been sitting for 5 minutes, with back supported and both feet placed on the floor, **systolic blood pressure (SBP) and diastolic blood pressure (DBP) will be measured twice** (1 to 2 minutes apart) using a validated device with an appropriately sized cuff ([Mancia et al 2007](#)); each BP measurement will be recorded in the source. In case the cuff sizes available are not large enough for the patient's arm, a sphygmomanometer with an appropriately sized cuff may be used.

If possible, assessments should be performed per patient by the same study center staff member throughout the study.

Normal blood pressure will be defined as a SBP of 90 to < 120 mmHg, and a DBP of 60 to < 80 mmHg under the measurement conditions outlined above. Notable blood pressure will be hypertension (SBP of \geq 140 mmHg and/or DBP of \geq 90 mmHg) or hypotension (SBP of < 90 mmHg and/or a DBP of < 60 mmHg). A blood pressure indicative of pre-hypertension (SBP of 120 to < 140 mmHg and/or DBP of 80 to < 90 mmHg) will not be regarded as notable ([Chobanian et al 2003](#)).

A normal pulse rate will be defined as a rate of 60 to 100 beats per minute (bpm) under the measurement conditions outlined above. Notable pulse rates are a rate below 60 bpm (bradycardia) or above 100 bpm (tachycardia).

Whether action needs to be taken to address notable vital signs will be decided by the Investigator, taking into account the overall status of the patient. No specific action is foreseen as part of the study protocol.

6.5.3 Height, weight, waist and hip circumference

Height and body weight will be measured at the times indicated in [Table 6-1](#). Height and body weight will be measured in indoor clothing, but without shoes.

If possible, body weight assessments should be performed by the same study center staff member and using the same scale throughout the study.

Waist and hip circumference will be measured at the times indicated in [Table 6-1](#). According to the World Health Organization (WHO) data gathering protocol ([STEPwise approach to surveillance, 2008](#)), the waist circumference should be measured at the midpoint between the lower margin of the last palpable rib and the top of the iliac crest, using a stretch resistant tape that provides a constant 100 g tension. Hip circumference should be measured around the widest portion of the buttocks, with the tape parallel to the floor.

For both measurements, the individual should stand with feet close together, arms at the side and body weight evenly distributed, and should wear little clothing. The patient should be relaxed, and the measurements should be taken at the end of a normal expiration. Each measurement should be repeated twice; if the measurements are within 1 cm of one another, the average should be calculated. If the difference between the 2 measurements exceeds 1 cm, the 2 measurements should be repeated.

6.5.4 Laboratory evaluations

Patients should avoid smoking within the hour preceding blood draws.

A central laboratory will be used for analysis of all specimens unless otherwise noted (e.g. urine dipsticks will be locally used). Details on the collections, shipment of samples and reporting of results by the central laboratory are provided to Investigators in the laboratory manual. The laboratory manual should also be consulted for the identification of notable values.

The Investigator will decide whether action needs to be taken to address notable laboratory values, taking into account the overall status of the patient. No specific action is foreseen as part of the study protocol.

6.5.4.1 Hematology

Hematology assessments will include hemoglobin, hematocrit, red blood cell (RBC) count, WBC count with differential (neutrophils including bands, lymphocytes, monocytes, eosinophils, basophils) and platelet count. Hematology assessments will be measured at all scheduled study visits within the visit window specified in [Table 6-1](#).

6.5.4.2 Clinical chemistry

Serum chemistry will include urea, creatinine, total bilirubin, alanine aminotransferase (ALT), aspartate aminotransferase (AST), gamma glutamyl transferase, and alkaline phosphatase (ALP). Serum chemistry will be measured at all scheduled study visits within the visit window specified in [Table 6-1](#).

6.5.5 Pregnancy and assessments of fertility

A serum β -hCG test will be performed in all pre-menopausal women as shown in [Table 6-1](#).

All pre-menopausal women who are not sterile at Screening will also have a urine pregnancy test performed locally as indicated in [Table 6-1](#).

Any woman with a confirmed positive pregnancy test during Screening is not eligible for enrollment.

A positive urine pregnancy test during the treatment periods of the study requires immediate interruption of study drug until serum β -hCG is performed and found to be negative. If the serum β -hCG test is positive, the study drug must be definitively discontinued, as described in [Section 5.6.2](#).

6.5.6 Appropriateness of safety measurements

The safety assessments selected are standard for this indication/patient population.

6.6 Other assessments

Health-related QoL(HR-QoL) assessments should be obtained as shown in [Table 6-1](#). Assessments can be collected either by using paper forms or with support of an electronic system.

6.6.1 Health-related quality of life

The impact of psoriasis on various aspects of a patient's HR-QoL will be assessed by the following validated instruments, each of which will be performed as indicated in [Table 6-1](#):

- NRS (itching, scaling and pain VAS)
- DLQI
- [REDACTED]
- EQ-5D[®]

- HAQ[®]-DI
- TSQM
- PBI

All these QoL assessments should be completed by the patient [REDACTED] before they see the study physician (Investigator or designee) who will perform the Investigator assessments. All assessments will be completed in the language the respondent is most familiar with, at the scheduled visit before the patient sees the Investigator for clinical assessments. The respondent should be given sufficient space and time to complete the questionnaires. The study coordinator should check the questionnaires for completeness and encourage the respondent to complete any missing responses. Prior to clinical examination, the Investigator should review the completed questionnaires for responses that may indicate potential AEs or SAEs.

If AEs or SAEs are confirmed, the Investigator must record the events as per the instructions in [Section 7](#).

Investigators should not encourage respondents to change the responses reported in the completed questionnaires.

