1.2 Purpose

Understanding the patient's perspective on their disease and treatment is an important component of clinical research and medical practice. The purpose of this patient centric study is to assess whether patient QoL outcomes are impacted by the exposure to prior treatment prior to starting treatment with secukinumab 300 mg s.c. in relation to the highest skin efficacy response expected at Week 16 and the skin efficacy response at Week 52. Feedback from patients on QoL outcomes will be assessed using a combination of dermatology-related, general health-related and psoriasis-related questionnaires: DLQI [REDACTED] EQ-5D[®] (overall health status); NRS (itching, scaling and pain VAS); HAQ -DI (functional ability and activity restriction - only in patients with concomitant PsA); TSQM (treatment satisfaction) and PBI (treatment benefit). The use of these PROs was discussed and agreed with dermatologist and patient representatives.

[REDACTED]

Finally skin efficacy and QoL will be investigated to generate hypotheses on possible correlations of relevance.

[figure not shown]
2 Study objectives

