If a patient refuses to return for these assessments or is unable to do so, every effort should be made to contact them, or a knowledgeable informant, by telephone or by sending appropriate correspondence (i.e. certified letter) immediately. At this contact, the safety (e.g. potential occurrence of AEs or SAEs) and the primary reason for the patient's premature withdrawal should be determined. As a minimum, these patients will be contacted for safety evaluations during the 4 weeks following the last dose of study drug or the 30 days point following the last study visit (whichever is later). Documentation of attempts to contact the patient should be recorded in the patient source documents.

Possible order of assessments:

Overall, it has been estimated that completion of PROs may take up to a maximum of approximately 60 minutes; it is recommended that the PROs might be administered to patients in the same sequence at each visit.

Suggested guidelines for conduct of the visit assessments are provided below:

- Patient to complete PROs prior to any other study assessments or influence by the study site in the following order:
 - NRS (itching, scaling and pain VAS)
 - DLQI
 - EQ-5D[®]
 - HAQ[®]-DI (only for patients with concomitant PsA)
 - TSQM
 - PBI
- 
- Investigator/qualified site staff to complete Investigator/qualified site staff assessments.

[figure not shown]

Recommended order is:

[figure not shown]
- IGA mod 2011
- PASI and BSA
- Physical examination
- All remaining study visit procedures (e.g. laboratory sample collection, vital signs measurements) must be completed prior to study drug dosing.
- Contact the electronic study system
- (Self-)Administration of study drug.

Table 6-1 Assessment schedule

[figure not shown]
Period	Scr	Treatment Period 1								Treatment Period 2					Uns ^d	Comments
		2	3	4	5	6	7	8	EOT1	10	11	12	13	EOT2		
Visit	1	2	3	4	5	6	7	8	9 ^{a, b}	10	11	12	13	14 ^c		
Week	-4 to BL	BL	1	2	3	4	8	12	16	20	24	36	48	52		
Recommended visit window (days)		±2	±2	±2	±2	±5	±5	±5	±2	±5	±5	±5	±5	±5		
Informed consent	X															
Demographics	X															
Inclusion/exclusion criteria	X	X														These assessments are supported by and stored within the source documentation. Data relating to inclusion/exclusion criteria are captured in the corresponding eCRF.
Smoking history	X															
Cardiovascular history	X															
Psoriasis: medical history / previous psoriasis therapies	X															

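### Section 6.6.1 lets an Investigator who also scores the skin read that visit's DLQI and NRS answers first, leaving IGA/PASI and the exploratory skin–QoL association open to bias

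*Protocol*

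**What the plan says.** The patient's answers are protected from the site. The order of assessments in Protocol Section 6 begins: "Patient to complete PROs prior to any other study assessments or influence by the study site". Section 6.6.1 has the questionnaires completed "before they see the study physician (Investigator or designee) who will perform the Investigator assessments", and adds: "Investigators should not encourage respondents to change the responses reported in the completed questionnaires".

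The same section then gives the Investigator a reading task: "Prior to clinical examination, the Investigator should review the completed questionnaires for responses that may indicate potential AEs or SAEs".

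The Section 6 list puts IGA mod 2011 first among the site assessments, then PASI and BSA, then the physical examination, then the remaining procedures, with dosing last. The questionnaire review does not appear in that list.

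On who rates the skin, Section 6.4.2 says: "The Investigator or trained qualified designee will complete the PASI assessment as indicated in" Table 6-1. For IGA, Section 6.4.1 says: "It is recommended that the same evaluator conducts the assessment throughout the study wherever possible". Neither section, nor the SAP, says whether the rater may see the PRO answers.

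On the use of the data, Protocol Section 1.2 says: "Finally skin efficacy and QoL will be investigated to generate hypotheses on possible correlations of relevance". The PASI and IGA response rates at Weeks 16 and 52 are secondary objectives (Section 2.2).

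**The concern.** IGA and PASI rest on judgement: 0–4 severity grades and estimated area percentages (Tables 6-3 and 6-4). The study is open label (Section 5.4), and Section 8.5 provides for no adjudication. A rater who has just read the DLQI and NRS forms knows how the patient feels before grading the skin. The overlap is direct for scaling: the patient rates it 0–10 on the NRS (Section 6.6.1.1), and the rater then grades it within PASI and IGA.

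If those answers pull the skin score, part of any agreement between skin and QoL comes from the procedure. The relation between the two appears in the study title and purpose, and the protocol's rationale (Section 3.2) says the extra QoL benefit of a 90% PASI reduction has yet to be shown. An avoidable link between the two measurements weakens what the study can say about it. The secondary PASI/IGA response rates are exposed too, as are the Baseline scores that decide eligibility (Section 4.1) and serve as the reference for PASI response.

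**Working it through.** **No plan figure to reproduce.** The documents give no number for this point. The sample size (323 in the smallest subpopulation, 1,615 in total) concerns the precision of the DLQI 0/1 proportion and is not touched by it.

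**Step 1: when do the two measurements coincide?** In Table 6-1 the PROs are collected at Baseline and Weeks 4, 12, 16, 24, 36, 48 and 52. IGA, PASI and BSA are scored at every visit. Every PRO visit is therefore also a skin-scoring visit, including Baseline, Week 16 and Week 52.

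**Step 2: where does the review fall?**

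- Section 6.6.1 puts it before the clinical examination and does not define that term. Nearby, the same paragraph has the forms completed before the patient sees the Investigator for clinical assessments. That favours reading the term as including IGA and PASI.
- The Section 6 list has a physical examination after IGA and PASI/BSA. If that is what Section 6.6.1 means, a review held between PASI/BSA and the physical examination satisfies both sections.
- Both orders are therefore compatible with the text. The first is the more natural reading and nothing excludes it.

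**Step 3: who is exposed?** The Investigator reviews the forms. The Investigator or a designee scores. Exposure arises when one person does both, or when the reviewer passes the answers on. The documents do not say how often this happens.

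**Step 4: direction and possible size.** All inputs here are assumptions. The 70% for DLQI 0/1 matches the rate expected in Section 9.7. The same rate is assumed for PASI 90, and the documents give neither the true association nor the degree of influence.

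*Binary illustration.* Both response rates p = 0.70, true phi = 0.30.

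- Both responses: p² + phi × p(1 − p) = 0.49 + 0.30 × 0.21 = 0.553.
- Each discordant cell: 0.70 − 0.553 = 0.147.
- If a fraction f of discordant PASI 90 results moves to agree with the DLQI, the joint cell becomes 0.553 + 0.147f, and phi = (joint − 0.49)/0.21.
- f = 0.10: joint 0.5677, phi = 0.0777/0.21 = 0.37.
- f = 0.20: joint 0.5824, phi = 0.0924/0.21 = 0.44.

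*Continuous illustration.* On standardised scores, if the rater adds weight w of the DLQI score to the skin score, the observed correlation is (r + w)/√(1 + 2wr + w²).

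| True r | w = 0 | w = 0.05 | w = 0.1 | w = 0.2 | w = 0.3 |
|---|---|---|---|---|---|
| 0.3 | 0.30 | 0.34 | 0.39 | 0.46 | 0.53 |
| 0.5 | 0.50 | 0.54 | 0.57 | 0.63 | 0.68 |
| 0.7 | 0.70 | 0.72 | 0.75 | 0.78 | 0.81 |

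Both models move the association upward when raters lean towards the PRO answers, and show no bias when they do not (f = 0 or w = 0).

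**Step 5: what is not exposed?** The DLQI and the other PROs are completed before the review, and Investigators are told not to encourage changes. This route runs from PRO to skin score only.

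**The case against.** The strongest reply is that the text does not require the skin to be scored with the answers known. Section 6.6.1 does not name IGA or PASI, Section 6 does not place the review, and a designee may score. A reader might infer that all IGA/PASI ratings are informed by the PROs and that the association is contaminated. The documents do not support that. They leave the route open and give no evidence of how often it is used. This part of the objection stands.

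It also stands that the skin–QoL correlation is described as hypothesis-generating, that Section 3.4 makes the variation in DLQI 0/1 across subpopulations the primary design aim, and that no visible primary or secondary objective is a correlation. The SAP section on other exploratory analyses (2.13) is not in the available text, so the planned association analysis cannot be checked.

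The binary illustration is a simplification. No rater makes a PASI 90 call: PASI combines 12 severity grades and four area scores, SAP Section 5.4.3 has the score calculated by the tablet, and response is then derived against Baseline. The response rates stay at 70% in that example only because the margins were set equal and the shifts symmetric. It would be wrong to infer that the bias can never show in the response tables.

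Finally, in an open-label study with AE questioning at each visit (Section 7.1), a rater can learn the patient's view in conversation, so moving the form review closes one channel and not all. That limits the benefit, but it does not justify keeping a written instruction that, on its natural reading, opens the channel.

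**Conclusion.** The point holds as an avoidable weakness in the order of procedures. On its natural reading, Section 6.6.1 allows an Investigator who also rates the skin to see that visit's DLQI and NRS answers first, and neither document prevents it. The secondary IGA/PASI outcomes and the exploratory skin–QoL association are open to bias. For the association the likely direction is upward, assuming that raters lean towards the patient's answers and not against them.

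The size is unknown. The shifts from 0.30 to 0.37 or 0.44 show what modest influence could do under the stated assumptions and are not estimates for this study. Exposure is partial and may differ between sites according to who scores.

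A reader might also infer that the primary result is compromised. It is not by this route: DLQI 0/1 at Week 16 and the other PROs are recorded before the review, and the sample size is unaffected. The change is worth making because it is cheap and keeps AE detection within the visit.

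**What to change.** 1. In Section 6.6.1, state that the questionnaire review for potential AEs/SAEs takes place after IGA mod 2011, PASI and BSA have been scored and entered, and before the physical examination and study drug administration.
2. In the Section 6 order list, insert the same step directly after PASI and BSA.
3. State that the person rating IGA, PASI and BSA does not look at that visit's PRO answers until the scores are entered. The coordinator's completeness check stays as it is.
4. For visits already conducted, report the sequence as a limitation of any skin–QoL association.

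This order works under either meaning of clinical examination: the review still precedes the physical examination and dosing at the same visit.

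The cost is a written amendment with the approvals that Section 11.1 requires, and training across about 250 centres in 30 countries (Section 3.1). That is more than editing a sentence, but it needs no extra staff, visit or procedure, and the change could be carried in an amendment made for other reasons.
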